STUDY PROTOCOL

Chinese Chronic Liver Failure Consortium Acute-on- Chronic Liver Disease and Failure Study ——a Prospective Multi-center Study in China, the Largest Hepatitis B Virus High-endemic Region

Clinicaltrials.gov ID: NCT02457637

Last updated date: 10 August 2018

OUTLINE

Abbreviations:.....	3
Background	4
Objective	6
Methods	7
Period I Recruitment:	7
Period II 28-Days Hospitalization and Observation:.....	8
Period III Clinic or Telephone Follow-up:	10
Statistical Analysis Plan.....	11
Trial size.....	11
Statistical methods	11
Outcome Measures	12
Primary Outcome Measures:.....	12
Secondary Outcome Measures:	12
Criteria:	14
Inclusion Criteria:.....	14
Exclusion Criteria:	14
Contacts/Locations	16
Reference	17

Abbreviations:

ACLF	Acute-on Chronic Liver Failure
CLIF	Chronic Liver Failure
CLIF-C OFs	Liver-chronic liver failure-Consortium Organ Failure score
HBV	Hepatitis B Virus
CANONIC in Cirrhosis	Chronic Liver Failure (CLIF) Acute-on Chronic Liver Failure
OFs	Organ Failure
AASLD	the America Association for the Study of Liver Disease
AD	Acute Decompensation
SOFA	Sequential Organ Failure Assessment Score
INR	International Normalized Ratio

Background

Acute-on chronic liver failure (ACLF) was first described by Japanese researchers in 1995[1]. In 2011, the American Association for the Study of Liver Disease (AASLD) and the European Association for the Study of the Liver (EASL) concluded that the core characteristics of ACLF were multiple organ failures and high short-term mortality[2]. In 2013, the EASL-CLIF (the European Association for the Study of The Liver-chronic liver failure) established the CLIF-SOFA[3] (chronic liver failure-sequential organ failure assessment) criteria of ACLF through a prospective multicenter study at 29 liver units in eight European countries for 1 year, with a focus on patients with alcoholic cirrhosis with acute decompensation (AD)[4]. In China, patients with acute deterioration of previously chronic liver disease were diagnosed with chronic severe hepatitis, until 2008 these patients had been termed "ACLF", due to the APASL reached a consensus of diagnostic criteria of ACLF[5, 6]. In the Asia-Pacific region, the majority of liver disease is viral hepatitis, while in western countries, it is alcoholic liver disease[7]. There is a sharp east-west divide with respect to the definition of ACLF, especially in the definition of chronic liver disease and its precipitating events[8, 9].

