The overall objective is to build a prospective multicenter clinical patient cohort representing Eastern-type ACLF in patients with chronic liver disease (cirrhotic and non-cirrhotic) of various etiologies, accompanied by AD or ALI, to characterize disease progression and establish appropriate diagnostic criteria.

Methods

Period I Recruitment:

The investigators plan to enroll 2000-3000 consecutive patients from January to December 2015. The research will be carried out in about 14 Chinese national wide liver centers each of whose total beds are around 500. Only chronic liver disease patients of various etiologies with AD or ALI will be enrolled. Then we will scan all of the enrolled patients and exclude those who fit our exclusion criteria.

Every patient remained will have a unique number. As soon as they are hospitalized, name, age, sex, ID (identification) number, telephone number, e-mail address, WeChat (a popular mobile phone text and voice messaging communication service) number, family address, and degree of education will be collected. The investigators will get the history and etiology of their liver disease, such as hepatitis B, alcoholic liver disease, and autoimmune liver disease. For viral hepatitis, the investigators will ask how antiviral therapy is conducted. The investigators will ascertain if the patients have a history of cirrhosis and for how long. The investigators will ascertain if the patients have any of the following predisposing factors: HBV reactivation, bacterial infection, active alcohol intake, HBV superimposed by other hepatitis viruses, gastrointestinal bleeding, portal vein thrombosis, surgery, intake of hepatotoxic drugs or herbs, or physiological exhaustion. The

investigators will establish the main cause of admission: gastrointestinal bleeding, hepatic encephalopathy, ascites, bacterial infection, jaundice or ALL. The investigators will determine whether the patients have chronic disease such as hypertension, coronary heart disease, diabetes, chronic renal disease, or connective tissue disease.

Period II 28-Days Hospitalization and Observation:

During hospitalization, data will be collected at 1, 4, 7,14, 21 and 28 days (or last visit date, if the patient is hospitalized less than 28 days), and 24h prior to death or LT (if the patient dies or has LT) and focus on the following three aspects.

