Period III Clinic or Telephone Follow-up:

Patients will be followed up regularly after discharge. When the patients die during follow-up, the time of death and main cause of death will be noted.

When the patients undergo LT during follow-up, the time of LT and the results of hepatic pathology will be noted.

Follow-up is by clinical visiting or telephone call depending on whether the patient can attend the clinic. Clinical follow-up is once a month for 2 years adding to 24 visits. The time of visit will be recorded. Antiviral therapy and alcohol intake will be monitored (if the patient has). Laboratory tests include routine blood tests, liver and renal function test, coagulation test, CRP and PCT. B ultrasound will be done to monitor cirrhosis (or fibrosis) and hepatocellular carcinoma. Telephone follow-up will be at 28 days, 3, 6,9, 12, 15, 18, 21 and 24 months. The investigators will determine whether there are new complications (e.g. gastrointestinal bleeding, hepatic encephalopathy, ascites, bacterial infection) and hepatocellular carcinoma.

Statistical Analysis Plan

Trial size

This is an exploratory, observational study, and anticipated size for this study is 2000-3000 patients.

Statistical methods

Refer to the CANONIC study, at the beginning we will focus on (but not limit in) the relationship between 6 parameters (TB, INR, Creatinine, SpO₂/FiO₂, mean arterial pressure and West-Haven grade), one for each organ/system, from CLIF-C OFs and 28-days or 90-days mortality and LT rate. Descriptive statistics, mean and standard difference, will be used to describe continuous variables, and frequency and percent will be to describe categorical variables (such as gender). Statistical significance ($P < 0.05$). In univariate statistical comparisons, the chi-square test will be used for categorical variables, T-test and Mann-Whitney test for continuous variables. Risk ratio (RR) will be used to evaluate and establish the cutoff value for each organ/system. Multivariate logistic regression, Cox' s PH models and other exploratory models would be used in the establishment of our ACLF prognostic scoring systems. The area under the ROC (AUC) will be used to compare the predictive value of ours with others. LT patients will be considered as censored and the survival function would be adjusted for the risk of liver transplantation at each study time point.

Outcome Measures

Primary Outcome Measures:

1. Short Term Mortality & Liver Transplantation Rate

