Description: Mortality & Liver Transplantation Rate will be calculated and reported at 28 days, 90 days, 180 days, 1 year, 2 year and 3 years after enrollment. Among them, the 28-day and 90-day mortality rates are the focus of our observation.

Time Frame: up to 3 years.

Secondary Outcome Measures:

2. The appearance and number of organ failure

Description: The appearance and number of organ failure (including liver, coagulation, renal, circulation, brain, respiratory system) will be evaluated and reported at 1, 4, 7, 14, 21 and 28 days (or last visit) during patients' hospitalization.

Time Frame: Up to 28 days.

3. Biochemical Parameters

Description: Serum bilirubin, international normalized ratio, serum creatinine, alanine aminotransferase, aspartate aminotransferase, alkaline phosphatase, γ -Glutamyltransferase, white blood cell count, neutrophil count and hemoglobin will be collected and reported at 1, 4, 7, 14, 21 and 28 days (or last visit) during patients' hospitalization.

Time Frame: Up to 28 days

4. Models for Disease Severity

Description: MELD score, MELD-Na score, CLIF-SOFA score, SOFA score and APACHE scores will be calculated and reported at 1, 4, 7, 14, 21 and 28 days (or last visit) during patients' hospitalization.

Criteria:

Inclusion Criteria:

1. Inpatient (hospitalization >1 days) (including patient in emergency observation wards);
2. Chronic liver disease patients including non-alcoholic fatty liver disease patients, chronic liver hepatitis patients without cirrhosis, compensated cirrhosis patients and decompensated cirrhosis patients;
3. Having acute liver injury [ALT (alanine aminotransferase) > 3NL (normal level), AST (aspartate aminotransferase) > 3NL or TB (total bilirubin) > 2NL within 1 week before enrollment] or acute decompensation [having ascites, hepatic encephalopathy, bacterial infection, gastrointestinal bleeding or jaundice (TB > 5NL) within 1 month].

Exclusion Criteria:

1. pregnancy;
2. hepatocellular carcinoma or other liver malignancies;
3. malignancy of other organs;
4. severe chronic extrahepatic disease including chronic obstructive pulmonary disease combined with respiratory failure, coronary heart disease with cardiac function level 3 (NYHA), myocardial infarction in the 3 months before admission, diabetes with severe complications and chronic kidney disease with end-stage renal failure;

5.receiving immunosuppressive drugs for reasons other than chronic liver disease;

Contacts/Locations

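### The primary outcome includes 3-year mortality and transplantation rates, but the written follow-up stops at about month 24

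*Combined protocol and SAP*

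**What the plan says.** Under Primary Outcome Measures, the mortality and liver transplantation (LT) rates "will be calculated and reported at 28 days, 90 days, 180 days, 1 year, 2 year and 3 years after enrollment". The same entry repeats the horizon: "Time Frame: up to 3 years". It also sets a priority: "Among them, the 28-day and 90-day mortality rates are the focus of our observation".

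The section on Period III, Clinic or Telephone Follow-up, gives the contact schedule:

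- Clinic: "Clinical follow-up is once a month for 2 years adding to 24 visits".
- Telephone: "Telephone follow-up will be at 28 days, 3, 6,9, 12, 15, 18, 21 and 24 months".
- Deaths: "When the patients die during follow-up, the time of death and main cause of death will be noted". LT is handled in the same way, with time and pathology noted when it happens during follow-up.

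Period III opens with a general statement that patients are followed regularly once discharged. It gives no end date and adds no contact beyond the two schedules. No registry linkage, record search or later status check appears elsewhere in the document.

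**The concern.** The 3-year horizon is stated twice, in the outcome description and in its time frame, so it does not read as a slip. Both follow-up routes end about a year earlier.

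The Statistical methods section plans Cox models and a survival function with LT patients censored. Under such methods a patient who is event-free at the last planned contact is censored there, and the curve has no support at month 36. A simple proportion or a logistic model does not avoid the problem, because either needs known status at month 36.

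The plan does not say how a 3-year figure would otherwise be obtained. If unobserved patients were counted as event-free, the rate would be biased downward. If it relied on unplanned reports of death or LT, ascertainment would be selective. The document plans neither, but it leaves both open.

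**Working it through.** **Reproducing the plan's own figure.** Monthly visits for 2 years: 12 × 2 = 24. This matches the stated number of clinic visits and confirms that the clinic route ends after 24 months.

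**Last planned contact.** The rates run from enrollment. The clinic visits appear to start after discharge, so two clocks are considered.

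- Enrollment clock: last telephone call and last clinic visit at month 24. Gap: 36 − 24 = 12.0 months.
- Clinic clock starting at a day-28 discharge (a scenario; the document does not cap the hospital stay): 28 / 30.44 = 0.92 month; 24 + 0.92 = 24.92; gap 36 − 24.92 = 11.08 months.

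**Coverage of each primary time point.**

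| Time point | Month | Within the written schedule? |
|---|---|---|
| 28 days | 0.92 | yes |
| 90 days | 2.96 | yes |
| 180 days | 5.91 | yes |
| 1 year | 12 | yes |
| 2 years | 24 | yes, at the last telephone call; no visit window is stated |
| 3 years | 36 | no |

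One of six is not covered.

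**What the planned data can say at month 36.** With censoring at the last planned contact, 0 patients are at risk and 0 events can be observed from then to month 36. Without extrapolation, 3-year mortality is bounded only between the 2-year value and 100%.

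An illustration with assumed figures that are not in the document: let m be 2-year mortality and h the risk of death in year 3 among survivors. Then 3-year mortality = 1 − (1 − m)(1 − h).

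- m = 30%: h = 2%, 5%, 10% gives 31.4%, 33.5%, 37.0%.
- m = 50%: h = 2%, 5%, 10% gives 51.0%, 52.5%, 55.0%.

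The planned data cannot tell the values within either row apart.

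**Calendar.** Period I Recruitment says: "The investigators plan to enroll 2000-3000 consecutive patients from January to December 2015". The title page says: "Last updated date: 10 August 2018". If enrollment ran as planned:

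- Last planned contact: 31 December 2015 + 24 months = 31 December 2017; + 28 days = 28 January 2018 under the day-28 scenario. Both precede the document date.
- Month 36 falls between January and December 2018.
- Assuming even accrual (not in the document), 1 January to 10 August 2015 is 222 days, so 222 / 365 = 60.8% were past month 36 at the document date. The remaining 143 / 365 = 39.2% were not: 2000 × 143/365 = 784 to 3000 × 143/365 = 1175 patients.
- If the share past month 36 was instead 45–75%, the number not yet there is 2000 × 0.25 = 500 to 3000 × 0.55 = 1650.

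These counts only separate patients for whom a month-36 check would be retrospective from those for whom it would be prospective. They are not a bias estimate. They also count everyone enrolled, so they exceed the number needing a check.

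**The case against.** The strongest reply is that this matters little. The outcome is titled as a short-term rate, the 28-day and 90-day results are the stated focus, the study is described as exploratory and observational, and the organ-failure cutoffs and prognostic score start from 28- or 90-day outcomes. All of that is true and limits the consequence. It does not remove the mismatch, because the 3-year rate is listed under the primary outcome.

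Second, the opening sentence of Period III has no end date, so later contact is not ruled out. That is fair as far as it goes. The sentence does not schedule any contact, however, and the schedules that follow it stop at month 24. The claim is therefore about what is specified; the document does not show what was done after month 24.

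Third, the Cox models are assigned to building the prognostic score and not to the reported rates. That is correct, but any method for a 3-year rate needs status at month 36.

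Fourth, dropping the 3-year point would be a late change to a stated primary outcome, while a single status check is feasible. This has weight. The document supports either route, and the order of preference is a judgment.

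Finally, the accrual counts and the day-28 clock rest on assumptions. They do, and the conclusion does not depend on them.

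**Conclusion.** The concern holds. The primary outcome section and Period III disagree on the length of follow-up, and a stated primary time point cannot be estimated from the data the plan describes without extrapolation. The size is 1 of 6 time points, with about 11.1 to 12.0 months uncovered and no patient under planned observation at month 36.

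The conclusion assumes only that the two schedules are the full follow-up plan, since no other is given. Elapsed time is not the obstacle: under the planned enrollment window, the document date falls about 2.6 to 3.6 years after enrollment. What is missing is a written means of ascertainment. The short-term results, cutoffs and score are unaffected. The mismatch should be fixed, but it does not threaten the study's main aims.

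**What to change.** Reconcile the Primary Outcome Measures with Period III by one of two routes.

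1. **Recommended: end at 2 years.** Remove the 3-year point, set the time frame to 2 years, and record this as an outcome change with its date and reason. This matches the follow-up as written. The cost is one documented change and the loss of the long-term figure.
2. **Keep 3 years.** Add to Period III one month-36 check of vital status and LT for all patients not known to have died or been transplanted. Record the date of any death or LT, obtain it retrospectively where month 36 has already passed, and censor patients who cannot be reached at their last contact. The cost is one check per such patient, using the telephone, e-mail, WeChat and address details already collected at admission, with some loss to non-contact.

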The first aspect is evaluation of organ failure. The circulatory system will be evaluated by measuring heart rate and blood pressure and use of vasopressors. Renal function will be evaluated by serum creatinine or renal replacement therapy. Coagulation function will be evaluated by INR (international normalized ratio of prothrombin time). Liver function will be evaluated by serum total bilirubin. The respiratory system will be evaluated by the ratio of oxyhemoglobin saturation and fraction of inspired oxygen. The nervous system will be evaluated by the grade of hepatic encephalopathy. Bacterial infection, including pneumonia, urinary tract infection, spontaneous bacterial peritonitis, spontaneous bacteremia, and cellulitis will be evaluated by positive culture results or imaging findings.

Systemic inflammatory reactive syndrome, sepsis, severe sepsis and septic shock will also be assessed. Gastrointestinal bleeding before and after admission, treatment with diuretics, and paracentesis will be recorded. The investigators will establish whether ascites and hepatic encephalopathy can be medically controlled.

The second aspect is laboratory examinations. Tests at admission will include routine blood, urine and stool tests, liver and renal function tests, blood electrolytes, blood-gas analysis, blood glucose, coagulation test, C-reactive protein (CRP), procalcitonin (PCT), HBV antibodies and antigens, anti-hepatitis A (IgM), HBV-DNA, anti-hepatitis E (IgM), anti-hepatitis C, and immunoglobulins (IgA, IgG, IgM and IgM-4). Tests at other times will include blood, urine and stool routine tests, liver and renal function tests, blood electrolytes, blood glucose, coagulation test, CRP and PCT (procalcitonin). Tests optionally done during hospitalization will include autoantibody measurement, blood culture (if the patients have fever and shivering), sputum culture (if there is suspicion of pulmonary infection), middle urine cultivation (when there is suspicion of urinary tract infection) and ascites culture (when there is suspicion of spontaneous bacterial peritonitis).

The third aspect is imaging. During hospitalization, thoracic X ray or computed tomography (CT) will be done to diagnose pulmonary infection. Abdominal CT (enhanced when necessary), B ultrasound and Fibro-Scan or

other elastography will be done to diagnose cirrhosis (or fibrosis), portal thrombosis, esophageal and gastric varices and hepatocellular carcinoma.

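### Does listing blood gas only at admission undermine the SOFA and APACHE scores planned on six days?

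*Combined protocol and SAP*

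**What the plan says.** Item 4 under Secondary Outcome Measures lists MELD, MELD-Na, CLIF-SOFA, SOFA and APACHE, all on the same days: "SOFA score and APACHE scores will be calculated and reported at 1, 4, 7, 14, 21 and 28 days (or last visit". No APACHE version is named, and no components are given for any score.

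Period II of the Methods sets the collection days: "During hospitalization, data will be collected at 1, 4, 7,14, 21 and 28 days", with one more collection in the 24 hours before death or transplantation. It divides the data into three parts.

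- **Organ failure.** "The first aspect is evaluation of organ failure". Here "The respiratory system will be evaluated by the ratio of oxyhemoglobin saturation and fraction of inspired oxygen", and the nervous system is judged by encephalopathy grade.
- **Laboratory tests.** The admission set contains "liver and renal function tests, blood electrolytes, blood-gas analysis, blood glucose, coagulation test". For later days the text reads "Tests at other times will include blood, urine and stool routine tests, liver and renal function tests, blood electrolytes, blood glucose, coagulation test", followed by CRP and procalcitonin. Blood gas is absent. It is also absent from the conditional tests, where "Tests optionally done during hospitalization will include autoantibody measurement, blood culture" is followed only by other cultures.
- **Imaging.** Not relevant here.

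No coma scale appears anywhere. The Statistical methods section centres on six CLIF-C OFs parameters, which include SpO2/FiO2 and West-Haven grade. It plans an AUC comparison of the new score with others, without naming the comparators or the day on which they are scored.

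**The concern.** The outcome promises scores on six days, while the test schedule seems to supply some of their inputs on one day or on none. On the usual understanding (the documents do not say), SOFA and APACHE both use arterial oxygenation and a coma scale, and APACHE also has an acid-base item. Read that way, APACHE after day 1 would either be missing unless a blood gas was ordered clinically, or be built from fewer items than on day 1. Blood gases ordered clinically plausibly come from sicker patients, so the later summaries could describe a selected group. Scoring an unmeasured item as normal would pull the score down.

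Two consequences could follow. A table of APACHE by day could show a trend produced by changing inputs. And if SOFA or APACHE is among the unnamed AUC comparators, a weakened comparator would flatter the new score.

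**Working it through.** The plan gives no figure to reproduce, so the check sets the score schedule against the data schedule and counts. Day 1 is taken to be admission.

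| Input | Day 1 | Days 4, 7, 14, 21, 28 |
|---|---|---|
| Saturation/FiO2 | planned | planned |
| Encephalopathy grade | planned | planned |
| Blood gas | listed | not listed |
| Coma scale | not named | not named |
| Body temperature, respiratory rate | not named | not named |

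**Step 1, the counts.** Planned summaries: 5 scores × 6 days = 30.

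- Inputs differ between day 1 and later days, with SOFA scored on saturation/FiO2: APACHE only, 1 × 5 = 5, and 5/30 = 17%.
- The same, if SOFA is meant to use arterial oxygenation: 2 × 5 = 10, and 10/30 = 33%.
- Not in standard form on any day because no coma scale is named: 2 × 6 = 12, and 12/30 = 40%.
- If the intended versions already use the recorded inputs: 0 of 30 on both counts.
- MELD, MELD-Na and CLIF-SOFA (3 × 6 = 18 of 30) appear unaffected.

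Every non-zero figure depends on score definitions that the documents do not contain. The figures count table cells. They do not measure patients affected, bias or precision.

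**Step 2, is the test list complete?** The argument needs Period II to be a full list of variables. On the same usual definitions, APACHE also uses body temperature and respiratory rate, and Period II names neither as a measurement, even at admission. A strict reading would therefore make APACHE unscorable on all 6 days, day 1 included, and not only on the later 5. The section also requires assessment of the systemic inflammatory response, sepsis and septic shock without listing the measurements these need. Both lists are phrased as what the tests will include, which does not exclude others. If temperature and respiratory rate are assumed to come from routine charts, a blood gas or coma scale may come from there too.

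**Step 3, which analysis would suffer?** The Statistical methods section plans no change-from-day-1 or longitudinal analysis of any score. The AUC comparison concerns prediction of outcomes timed from enrollment, so day 1 is the natural scoring day. At day 1 blood gas is listed, and the later gap does not enter. The coma-scale gap is the same on every day and produces no drift.

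**Step 4, would a restriction help?** The obvious repair is APACHE on day 1 only, with any score that has an unmeasured item set to missing. It would drop 5 of the 30 summaries without looking at what was recorded. By Step 2, applied strictly to the listed tests, it would also remove the day-1 APACHE it means to keep. Recruitment was planned for January to December 2015 and the document was last updated in August 2018. On that timetable the 28-day data already existed, so availability could be checked directly.

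**The case for a change.** The best case for a change is that the plan cannot be executed unambiguously. It refers to APACHE scores in the plural with no version. It lists SOFA separately from CLIF-SOFA, so it evidently regards them as different scores, yet the neurological and respiratory measures it records are the ones it attributes to CLIF-C OFs. The other admission-only tests are mainly viral markers and immunoglobulins, so blood gas stands out as the acute physiological test that is not repeated. With about 14 centres, unstated inputs leave room for inconsistent scoring. A clarifying sentence would cost little and need no extra sampling.

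Part of this stands. The versions, input sources and rule for unmeasured items are indeed not stated, and a report that left them out would be hard to interpret. The risk that later blood gases come from sicker patients is also real, though it is an inference and not something the documents state.

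The between-centre worry is weaker. Every centre is given the same respiratory and neurological measures, and nothing says that centres calculate the scores themselves. The AUC worry is conditional twice over: SOFA or APACHE must be a comparator, and for the blood-gas gap to matter it must be scored after day 1.

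**Conclusion.** The schedule facts are correct, but they do not show a fault that calls for a change to the plan. What remains is missing detail on a descriptive secondary outcome in a study that calls itself exploratory and observational. Competent analysts fill such a gap in the ordinary course of work: they name the versions, say where each input came from, label SOFA as modified if surrogates are used, do not score unmeasured items as normal, and show the number evaluable on each day. For an AUC comparison they would use day-1 scores in the same patients as the new score.

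The size is at most minor. Between 0 and 10 of 30 summaries could have inputs that differ between day 1 and later days (5 on the most natural reading), and between 0 and 12 of 30 could be non-standard in form. These ranges rest on assumed score definitions and on day 1 being admission. Absence from the schedule does not establish absence from the data. Cutting later-day APACHE from the plan would be a debatable trade with no clear gain. The primary outcome and the six CLIF-C OFs parameters are not affected on any reading.
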